**Sponsor: Sensi Biotherapeutics****Protocol: SNS301-2-2**

SCCHN	Squamous cell carcinoma of the head and neck
SD	Stable disease
SNS-301	HAAH bacteriophage lambda constructs: HAAH-1 $\lambda$ transaminase
SOC	System organ class
SUSAR	Suspected unexpected serious adverse reaction
TNF	Tumor necrosis factor
TSH	Thyroid stimulating hormone
TT	Thrombin Time
ULN	Upper limit of normal
WBC	White blood count

Approved

Sponsor: Sensi Biotherapeutics

Protocol: SNS301-2-2

## 1. PURPOSE

This Statistical Analysis Plan (SAP) describes the methods to be used in the analysis of trial data from clinical protocol 'An Open-Label, Multi-Center Trial of SNS-301 Added to Pembrolizumab in Patients with Locally Advanced Unresectable or Metastatic/Recurrent Squamous Cell Carcinoma of the Head and Neck' in order to answer the trial objective(s), and is based on the trial protocol SNS301-2-2, dated November 6, 2020 (Version 4.0).

Populations for analysis, data handling rules, statistical methods, and formats for data presentation are described within this document. The statistical analyses and summary tabulations described in this SAP will provide the basis for the results sections of the CSR for this trial. The SAP outlines any differences in data analysis methods relative to those planned in the trial protocol. Any changes to the data analysis methods after the SAP is finalized will be described in the CSR.

## 2. OVERALL STUDY DESIGN AND OBJECTIVE

### 2.1 Trial Objectives

#### *Primary Objective*

- To determine the safety and tolerability of SNS-301 delivered by intradermal injection (ID) using the 3M® hollow microstructured transdermal system (hMTS) device in patients with locally advanced unresectable or metastatic/recurrent SCCHN.
- To evaluate the anti-tumor activity of SNS-301 delivered by intradermal injection (ID) using the 3M® hollow microstructured transdermal system (hMTS) device in addition to pembrolizumab in patients with locally advanced unresectable or metastatic/recurrent SCCHN

#### *Secondary Objective*

- To evaluate preliminary immune response to SNS-301 delivered by intradermal injection (ID) using the 3M® hollow microstructured transdermal system (hMTS) device in addition to pembrolizumab in patients with locally advanced unresectable or metastatic/recurrent SCCHN.

#### *Exploratory Objective*

- To evaluate tumor and immune biomarkers and their association with treatment outcome (antitumor activity and/or safety) in patients with locally advanced unresectable or metastatic/recurrent SCCHN.

[figure not shown]
### 2.2 Trial Design and Trial Procedures

Sponsor: Sensi Biotherapeutics

Protocol: SNS301-2-2

This is a Phase 1/2, open-label, multi-center trial to evaluate the safety, immunogenicity and preliminary clinical efficacy of SNS-301 delivered by intradermally in addition to pembrolizumab in patients with locally advanced unresectable or metastatic/recurrent SCCHN. The trial population consists of patients with locally advanced unresectable or metastatic/recurrent SCCHN who are currently receiving a checkpoint inhibitor (CPI) therapy (anti-PD1 and anti-PD-L1 agents) (Cohort A) or are naïve to CPI therapy (Cohort B). The cohorts for this study are highlighted below:

Each cohort will enroll up to approximately 30 patients. Approximately 60 patients will be enrolled over two cohorts at up to 15 institutions within the United States. The study enrollment is expected to last approximately 18-24 months.

Patients who are currently receiving CPI therapy must have a best response of stable disease (SD) or first evidence of progressive disease (PD) after a minimum of 12 weeks of a CPI therapy. Patients receiving first-line pembrolizumab monotherapy must be PD-L1 positive. Patients receiving a CPI other than pembrolizumab will be switched over to pembrolizumab at the time of entering this study.

A tissue sample is required for entry onto the study with either a fresh biopsy or archival tissue from a previous biopsy. Ideally, a pre-treatment tissue sample obtained after initiation of ongoing CPI therapy and before first dose of SNS-301 and pembrolizumab on this current clinical trial will be collected. Patients unable to provide pre-treatment biopsy while on CPI will be evaluated on a case-by-case basis for enrollment pending Sponsor consultation.

Patients are requested to provide archival tissue from a prior biopsy or surgery that is treatment-naïve including prior 1) chemotherapy, radiation and 2) anti PD(L)-1 treatment-naïve, pending availability. An on-treatment biopsy is required when medically feasible, after the second or third dose of treatment around treatment week 6. Additionally, up to two optional biopsies may be obtained at any time during the study, if medically feasible. For patients who progress as determined per RECIST1.1/iRECIST criteria, an optional biopsy will be obtained at the time of disease progression. The Sponsor may request digitized scans from patients to confirm response.

CONFIDENTIAL

Statistical Analysis Plan

Page 8 of 45

Version 1.0

Sponsor: Sensi Biotherapeutics

Protocol: SNS301-2-2

This study will employ a Simon 2-stage design, with 15 evaluable patients (i.e. meeting the definition for the efficacy evaluable analysis set; at Week 12 for both cohorts. Non-evaluable patients will be replaced.

The safety run-in will be performed using a modified rolling six design which will enroll up to six patients (safety analysis patients). These patients may contribute to the first 15 in stage 1, assuming they meet the definition for evaluable for efficacy. The end of the safety run-in period is defined as the earliest of the following:

- The first three patients have all completed Week 6 with no DLTs experienced by any of the safety runin patients in that cohort (up to six); enrollment may then proceed through stage 1;
- All six patients of the safety run-in phase, have completed week six with only one patient having experienced a DLT; enrollment may then proceed through stage 1;
- Two or more of the safety run-in patients, have experienced DLTs prior to completing Week 6; enrollment will be suspended.

If at least one responder (ORR per iRECIST) is observed in the first 15 evaluable patients (i.e. meeting the definition for the efficacy evaluable population) by Week 12, then the study will continue to Stage 2 and enroll up to 15 additional patients. If at least 4 responders are observed overall, further research will be deemed warranted.

[figure not shown]
There will be a waiting period of one week between enrollment of the first patient and the second patient because this trial is treating patients with SNS-301 and pembrolizumab for the first time. The interim efficacy assessment, for each cohort, will occur after 15 patients were enrolled and completed the 12-week follow-up period. A safety review will occur in parallel to the efficacy assessment of the first 15 patients

The trial will be stopped if any adverse experience of any related death, grade 4 autoimmune toxicity or any grade 4 toxicity that is considered to have a causal relationship to study drug should occur. These events will be submitted to regulatory agencies within the expedited safety reporting criteria.

The clinical trial will be considered completed when all patients have had their three-year follow-up visit, death, lost to follow-up, withdrawal of consent, or when the Sponsor deems the study completed, whichever comes first.

The study schema is presented in Figure 1:

Figure 1: Study Schema

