This study will employ a Simon 2-stage design, with 15 evaluable patients (i.e. meeting the definition for the efficacy evaluable analysis set; at Week 12 for both cohorts). The criteria for advancing to Stage 2 is described in Section 10.2. Non-evaluable patients will be replaced.

The safety run-in will be performed using a modified rolling six design which will enroll up to six patients (safety analysis patients). These patients may contribute to the first 15 in stage 1, assuming they meet the definition for evaluable for efficacy.

Once the first three patients of these six patients have completed Week 6 assessments, in the absence of any dose-limiting toxicity (DLT), enrollment may proceed through stage 1. However, if prior to the first three patients completing Week 6, a single patient from the first six experiences a DLT, then enrollment will be limited to six patients until all six patients have reached Week 6 and are assessed for DLT. If no additional patients, of these six, experience a DLT within the 6-week safety run in period, then enrollment may proceed to completion.

If a second of these first six patients experiences a DLT within the first six weeks, enrollment will stop, and the Sponsor's medical monitor, in addition to the PI and Investigator(s) at the patients' site(s) will discuss the case, and a decision will be made whether to modify the trial or to cease further enrollment. If enrollment is ceased, it will only be reinitiated after amendment of the protocol and approval of the amended protocol by the IRB.

Safety run-in patients that withdraw from the study for reasons other than a DLT, prior to the end of the safety run-in period, will be replaced. The end of the safety run-in period is defined as the earliest of the following:

- The first three patients have all completed Week 6 with no DLTs experienced by any of the safety run-in patients in that cohort (up to six); enrollment may then proceed through stage 1;
- All six patients of the safety run-in phase, have completed week six with only one patient having experienced a DLT; enrollment may then proceed through stage 1;
- Two or more of the safety run-in patients, have experienced DLTs prior to completing Week 6; enrollment will be suspended.

DLTs are defined in the protocol section 9.3.9.

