To evaluate the primary endpoint of objective response rate per iRECIST at 12 weeks with a null hypothesis of an objective response rate (ORR) of 13.3% and an alternative hypothesis of an ORR of 29%, 30 patients in a two-stage design will be enrolled, with 15 patients in the first stage and 15 patients in the second stage. At the first stage analysis if at least 2 responses are observed out of 15 patients, the study may continue through the second stage. At the second stage analysis, if at least 7 responses are observed out of 30 total patients, the null hypothesis will be rejected and further research considered warranted. The overall power for objective response rate at 12 weeks is 80.1%. The overall type I error, the chance of incorrectly rejecting the null hypothesis is 9.2% (targeted alpha of 0.10). The probability of stopping at the first stage under the null hypothesis is 38.8%. The operating characteristics of this design are calculated using the exact binomial distribution.

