## **Cohort B**

To evaluate the primary endpoint of objective response rate per iRECIST at 12 weeks with a null hypothesis of an objective response rate (ORR) of 13.3% and an alternative hypothesis of an ORR of 29%, 30 patients in a two-stage design will be enrolled, with 15 patients in the first stage and 15 patients in the second stage. At the first stage analysis, if at least 2 responses are observed out of 15 patients, the study may continue through the second stage. At the second stage analysis, if at least 7 responses are observed out of the total 30 patients, the null hypothesis will be rejected and further research considered warranted. The overall power for objective response rate at 12 weeks is 80.1%. The overall type I error, the chance of incorrectly rejecting the null hypothesis is 9.2% (targeted alpha of 0.10). The probability of stopping at the first stage under the null hypothesis is 38.8%. The operating characteristics of this design are calculated using the exact binomial distribution.

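### SAP 2.2 states one go/no-go rule with no cohort named, and it is Cohort A's; it contradicts the Cohort B rule in SAP 2.4 and Protocol 10.2. Cohort B's PD-L1 entry requirement is also stated two ways.

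*SAP*

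**What the plan says.** SAP 2.2 first describes Cohorts A and B. It then sets out a Simon two-stage design with 15 evaluable patients, "meeting the definition for the efficacy evaluable analysis set; at Week 12 for both cohorts". The stage 1 rule follows with no cohort named: "If at least one responder (ORR per iRECIST) is observed in the first 15 evaluable patients" by Week 12, the study goes on to Stage 2 with up to 15 more patients. The final rule is "If at least 4 responders are observed overall, further research will be deemed warranted".

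SAP 2.4 gives each cohort its own rule. Cohort A (null 5%, alternative 18%) needs at least 1 of 15, then at least 4 of 30. Cohort B (null 13.3%, alternative 29%) may continue "if at least 2 responses are observed out of 15 patients", and "if at least 7 responses are observed out of the total 30 patients, the null hypothesis will be rejected". Protocol 10.2 agrees for Cohort B: "if at least 7 responses are observed out of 30 total patients, the null hypothesis will be rejected". The protocol section that corresponds to SAP 2.2 is Protocol 5.2. It states no thresholds and points elsewhere: "The criteria for advancing to Stage 2 is described in Section 10.2".

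On who enters Cohort B, inclusion criterion 3 (Protocol Synopsis and Section 6, Cohort B item b) allows study treatment as first-line therapy in PD-L1-positive patients or second-line therapy in PD-L1-negative patients. Protocol 9.2.13 and SAP 6.9 say that CPI-naïve patients must be PD-L1 positive before entry.

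**The concern.** Two sections of one SAP give different decision rules for the same cohort on the primary efficacy endpoint, and neither section is said to take precedence. The SAP change history records that Section 2 was revised after protocol Version 4.0, the amendment that added Cohort B, so the SAP 2.2 text is current. A programmer or committee member working from the design section would find a rule that appears to cover both cohorts and could apply it to Cohort B. Cohort B's null is much higher than Cohort A's (13.3% against 5%). A bar of 4 responses that is demanding for Cohort A is therefore undemanding for Cohort B: 4/30 = 13.3%, which is Cohort B's null rate itself.

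The PD-L1 conflict matters statistically because Cohort B's null has to describe the background response rate of the patients who are enrolled, and the documents define those patients in two ways.

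**Working it through.** Inputs are the thresholds, null and alternative rates in SAP 2.4 and Protocol 10.2, and the thresholds in SAP 2.2. Each stage has 15 patients.

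Formula: let X1 be the stage 1 responses, X2 the stage 2 responses, both Binomial(15, p), with a the stage 1 minimum and c the overall minimum.

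- P(success) = sum over x from a to 15 of P(X1 = x) × P(X2 ≥ c − x)
- P(early stop) = P(X1 < a)

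**Step 1: reproduce the plan's own figures.**

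| Cohort and rule | Quantity | Computed | Stated |
|---|---|---|---|
| A: ≥1/15, ≥4/30 | Type I error at 5% | 0.0582 | 6% |
| A | Power at 18% | 0.8002 | 80% |
| A | Early stop at 5% | 0.4633 | 46% |
| B: ≥2/15, ≥7/30 | Type I error at 13.3% | 0.0917 | 9.2% |
| B | Power at 29% | 0.8006 | 80.1% |
| B | Early stop at 13.3% | 0.3881 | 38.8% |

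All six agree with the stated values at the stated rounding. SAP 2.2's thresholds (a = 1, c = 4) are those of Cohort A.

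**Step 2: apply SAP 2.2's rule to Cohort B at p = 0.133.**

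Early stop = 0.867^15 = 0.1176.

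| x | P(X1 = x) | P(X2 ≥ 4 − x) | Product |
|---|---|---|---|
| 1 | 0.27053 | 0.32141 | 0.08695 |
| 2 | 0.29050 | 0.61191 | 0.17776 |
| 3 | 0.19311 | 0.88243 | 0.17040 |
| 4 | 0.08887 | 1 | 0.08887 |
| 5 | 0.02999 | 1 | 0.02999 |
| 6 or more | 0.00944 | 1 | 0.00944 |

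The products sum to 0.5634. Success at the null is 56% (9.2% under Cohort B's own rule), and early stopping is 12% (38.8% under its own rule).

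**Step 3: see which threshold matters.** At p = 0.133, ≥2/15 then ≥4/30 gives 0.4765, while ≥1/15 then ≥7/30 gives 0.0942. The final threshold accounts for nearly all of the difference.

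**Step 4: find where the two sections disagree for Cohort B.**

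- Exactly 1 response in the first 15: SAP 2.2 continues; SAP 2.4 does not.
- At least 2 in the first 15 and 4, 5 or 6 in 30: SAP 2.2 calls further research warranted; SAP 2.4 does not reject the null. At p = 0.133 this has probability 0.3848.

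These account for the whole gap: 0.0917 (success under both rules) + 0.3848 + 0.0869 (exactly 1 in stage 1, then at least 4 overall) = 0.5634. At 4/30, the exact 90% interval that the SAP plans for ORR runs from 4.7% to 28.0%, so it contains the 13.3% null.

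**PD-L1 entry, side by side.** A CPI-naïve, PD-L1-negative patient seeking second-line treatment meets item b of the Cohort B inclusion criterion and fails the requirement in Protocol 9.2.13 and SAP 6.9. Both readings cannot hold. According to the protocol's summary of changes, both protocol statements came in with Version 4.0, so neither is left over from a time before Cohort B existed.

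**The case against.** The strongest reply is that nobody need be misled. SAP 2.4 and Protocol 10.2 give the Cohort B rule under its own heading, tie it to the hypothesis test and state matching operating characteristics. SAP 2.2 is narrative and mentions no null or error rate. Most of this stands: the 56% depends on someone using SAP 2.2 for Cohort B. It does not remove the contradiction, because SAP 2.2 covers both cohorts and attaches a conclusion about further research to its rule. A figure follows the rule in SAP 2.2 and was not available for this check. If it shows thresholds by cohort, the sentence above it would still need a label.

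A reader might infer that Cohort B's type I error is really 56%. The documents do not support that; the planned design has 9.2%.

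A reader might also infer that the 13.3% null is too low, because Protocol 3.2.1.1 cites 19% for first-line PD-L1-positive patients when it introduces Cohort B, and Cohort B's own rule would succeed about 33% of the time at a true background of 19%. The documents do not support this either. The 19% has no stated time point or confirmation rule, and it would describe the whole cohort only if every patient were first-line and PD-L1 positive. The inclusion criterion also admits second-line PD-L1-negative patients. The same protocol section cites 13.3% for nivolumab in platinum-refractory disease, although it does not link that figure to Cohort B. The null may be right for a mixed cohort and is not shown to be an error.

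**Conclusion.** SAP 2.2 is wrong as written for Cohort B. It should be corrected, because it states a decision threshold for the primary efficacy endpoint that conflicts with SAP 2.4 and Protocol 10.2. If it were followed for Cohort B, the chance of declaring success at the 13.3% null would be about six times the stated value (0.563/0.092 = 6.1). These probabilities assume exactly 15 evaluable patients per stage, independent responses, a true rate equal to the null, and literal use of the SAP 2.2 thresholds. The sample size calculation needs no correction.

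The PD-L1 entry conflict is a second, separate contradiction. Its effect on the operating characteristics cannot be sized, because the documents give neither the expected PD-L1 mix nor a background rate for each group. It leaves open which population the 13.3% is meant to describe.

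**What to change.** 1. In SAP 2.2, label at least 1/15 and at least 4/30 as Cohort A's rule and add at least 2/15 and at least 7/30 for Cohort B. Alternatively, delete the thresholds and refer to SAP 2.4, as Protocol 5.2 does with Section 10.2. This changes wording only; no threshold, sample size or analysis changes.

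2. Reconcile the Cohort B inclusion criterion (Protocol Synopsis and Section 6) with Protocol 9.2.13 and SAP 6.9 on PD-L1 status. Which reading is intended is for the sponsor to decide. This is more than an edit, because it determines who may enter Cohort B and requires a protocol amendment as well as an SAP change.

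3. Once item 2 is settled, the sponsor should confirm that 13.3% still describes the background Week 12 response rate of the resulting population. If it does, the Cohort B thresholds stand. If it does not, the thresholds and their operating characteristics would have to be worked out again, so it cannot be promised in advance that items 2 and 3 leave the design unchanged.

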## 2.3 Treatments and Assignment to Treatments

### SNS-301 Dosing

- SNS-301 ( $1 \times 10^{11}$  dose/1ml) ID is administered using the 3M® hollow microstructured transdermal system (hMTS) device.
- Patients will receive SNS-301 on a staged schedule starting every three weeks for four doses, every six weeks for 6 doses and thereafter every twelve weeks.
- When pembrolizumab and SNS-301 are dosed on the same day, SNS-301 will be dosed approximately 1 hour after IV infusion of pembrolizumab for the first dose. Subsequent doses of SNS-301 and pembrolizumab can be dosed in any order.
- A 60 minutes observation period is recommended for the first dose on this study and 30 minutes for subsequent doses.

### Pembrolizumab Dosing

- A fixed dose of 200 mg pembrolizumab as an intravenous infusion over 30 minutes every 3 weeks or a fixed dose of 400 mg pembrolizumab, as an intravenous infusion over 30 minutes every 6 weeks will be administered. A sterile, non-pyrogenic, low-protein binding 0.2 micron to micron in-line or add-on filter will be utilized. A 60 minutes observation period is recommended for the first dose on this study and 30 minutes for subsequent doses.

Sponsor: Sensi Biotherapeutics

Protocol: SNS301-2-2

Patients will receive their study treatments until disease progression, unacceptable toxicity, deemed intolerable by investigator or up to 24 months in patients without disease progression.

There will be no SNS-301 dose reductions.

In case of non-DLT AE (grade 2 NCI-CTCAE V5.0 drug related AE), the dosing interval can be extended up to 42 days to allow the recovery from a related toxicity and the patient will resume at the same dose. If the patient experiences the same grade or higher toxicity and same grade requiring a dose-delay at the subsequent cycle, the patient should be discontinued from study treatment.

Should there be a clinically significant AE or SAE recorded relating to a patient receiving anticoagulants, such as clinically noted bleeding, administration of SNS-301 will be held until the AE/SAE returns to baseline. Should there be two individual events of SNS-301 interruption for the same patient, then SNS-301 will be discontinued after consultation with the Medical Monitor and Study Sponsor.

If a patient is unable to receive study treatment (e.g., due to COVID19) the dosing interval can be extended up to 42 days after consultation with the Sponsor and the rationale to be documented.

Treatment with SNS-301 may continue if pembrolizumab is discontinued by the Investigator, if prior to 24 months. If both study treatments are stopped for more than 42 days then the patient should be discontinued from study treatment and continue to the study follow up phase.

## 2.4 Determination of Sample Size

The sample size for each cohort and stage is based on Simon's two-stage design for tests of one proportion.

### Cohort A

To evaluate the primary endpoint of objective response per iRECIST at 12 weeks with a null hypothesis of an objective response rate (ORR) of 5% and an alternative hypothesis of an ORR of 18%, 30 patients in a two-stage design with 15 patients in the first stage and 15 patients in the second stage will be enrolled.

Subjects with evidence of disease progression or deemed unevaluable at 12 weeks will not be counted towards assessment of futility. At the first stage analysis if at least 1 response is observed out of 15 patients, the study will continue through the second stage. At the second stage analysis, if at least 4 responses are observed out of 30 total patients, the null hypothesis will be rejected, and further research considered warranted.

The overall power for the objective response rate at 12 weeks is 80%. The overall type I error, the chance of incorrectly rejecting the null hypothesis is 6% (targeted alpha of 0.10). The probability of stopping at the first stage under the null hypothesis is 46%. The exact binomial distribution is used in the operating characteristics of this design.

Sponsor: Sensi Biotherapeutics

Protocol: SNS301-2-2

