Trial Population: The trial population consists of patients with locally advanced unresectable or metastatic/recurrent SCCHN who are currently receiving a CPI therapy (Cohort A) or are naïve to CPI therapy (Cohort B). Patients who are currently receiving CPI therapy must have a best response of stable disease (SD) or first evidence of progressive disease (PD) after a minimum of 12 weeks of treatment with a CPI. Patients receiving first-line pembrolizumab monotherapy must be PD-L1 positive. Patients receiving a CPI other than pembrolizumab will be switched over to pembrolizumab at the time of entering this study.	 Sample Size: Approximately up to 30 patients will be enrolled into each cohort on the trial. This is a two-stage clinical trial with the primary efficacy endpoint of objective response per iRECIST. Patients enrolled in the first stage will need to be deemed evaluable at 12 weeks, meeting the definition for the efficacy evaluable analysis set; at least one dose of treatment and the Week 12 efficacy assessment or progression prior to Week 12. Approximately 15 patients may be enrolled in the first stage and evaluated for objective response (futility assessment) at 12 weeks. All patients will participate in the overall efficacy analysis. If warranted, based on response, up to an additional 15 patients may be enrolled in each cohort in the second stage.

See Section 10 for an explanation of the 2-stage enrollment.

[figure not shown]
The study enrollment is expected to last approximately 18-24 months.

Study Design:

This is a Phase 1/2, open-label, multi-center trial to evaluate the safety, immunogenicity and preliminary clinical efficacy of SNS-301 delivered intradermally in addition to pembrolizumab in patients with locally advanced unresectable or metastatic/recurrent SCCHN. A safety run-in will be performed using a modified rolling six design which will enroll up to 6 patients and these patients will be included in the first stage of trial assessments pending they meet criteria set forth above.

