10.2 Sample Size Determination

Adverse events will be continuously monitored. Among the first phase of 15 patients, for adverse events that occur at an incidence of 18% the probability of observing at least one event is approximately 95%. Among all 60 patients, for adverse events that occur at an incidence of 5% the probability of observing at least one event is approximately 95%.

The sample size for each cohort and stage is based on Simon's two-stage design for tests of one proportion.

Cohort A

To evaluate the primary endpoint of objective response rate per iRECIST at 12 weeks with a null hypothesis of an objective response rate (ORR) of 5% and an alternative hypothesis of an ORR of 18%, 30 patients in a two-stage design with 15 patients in the first stage and 15 patients in the second stage will be enrolled. At the first stage analysis if at least 1 response is observed out of 15 patients, the study will continue through the second stage. At the second stage analysis, if at least 4 responses are observed out of 30 total patients, the null hypothesis will be rejected and further research considered warranted. The overall power for objective response rate at 12 weeks is 80%. The overall type I error, the chance of incorrectly rejecting the null hypothesis is 6% (targeted alpha of 0.10). The probability of stopping at the first stage under the null hypothesis is 46%. The operating characteristics of this design are calculated using the exact binomial distribution.

Cohort B

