### *Efficacy-Evaluable Analysis Set*

The Efficacy-Evaluable Analysis Set comprises all patients who receive at least 1 dose of the study treatment or component of the study treatment and have a post baseline response assessment per iRECIST at Week 12. Subjects who discontinued prior to Week 12 due to radiological disease progression will be included. Subjects who do not have a post baseline response assessment conducted will not be included in the analysis of efficacy.

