## 9.5 Interim Analysis and Data Monitoring

A Safety Committee will be formed to monitor safety on a periodic basis. The Safety Committee will meet at the completion of the safety run-in to review safety data collected from the point of first patient in (FPI) to review safety, or as needed. The safety data will include demographic data, adverse events, serious adverse events, and relevant laboratory data.

The interim efficacy assessment, for each cohort, will occur after 15 patients were enrolled and completed the 12-week follow-up period. The objective response rate, for each cohort, will be assessed at the completion of stage 1 of the 2-stage design, after 15 patients complete the 12-week follow-up period or discontinue prior due to disease progression. A safety review will occur in parallel to the efficacy assessment of the first 15 patients in each cohort.

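### A sentence in SAP 2.4 leaves progressors out of the Cohort A futility count, contradicting the rest of the SAP and the protocol; its effect depends on whether stage 1 would be refilled

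*SAP*

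**What the plan says.** The Cohort A paragraph of SAP 2.4 sets the two-stage rule: null ORR 5%, alternative 18%, 15 + 15 patients, continue with at least 1 response of 15, reject with at least 4 of 30. Between the sample size and the stage 1 rule it inserts: "Subjects with evidence of disease progression or deemed unevaluable at 12 weeks will not be counted towards assessment of futility".

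Other current text defines the 15 differently:

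- SAP 2.2 bases the move to stage 2 on at least one responder "observed in the first 15 evaluable patients (i.e. meeting the definition for the efficacy evaluable population) by Week 12".
- SAP 4, defining that set: "Subjects who discontinued prior to Week 12 due to radiological disease progression will be included".
- SAP 9.5, second interim sentence, assesses ORR "after 15 patients complete the 12-week follow-up period or discontinue prior due to disease progression". Protocol 10.5 has the same rule.
- The protocol synopsis describes a patient evaluable for stage 1 as having "at least one dose of treatment and the Week 12 efficacy assessment or progression prior to Week 12".
- Protocol 10.2, Cohort A, gives the stage 1 rule with no exclusion: "At the first stage analysis if at least 1 response is observed out of 15 patients, the study will continue through the second stage".
- SAP 2.4, Cohort B, also has none: "At the first stage analysis, if at least 2 responses are observed out of 15 patients, the study may continue through the second stage".

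SAP 1 says the SAP is based on protocol Version 4.0, so the protocol text above is its source.

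**The concern.** The SAP gives two answers to who makes up the 15 at Cohort A's only formal futility look. Under SAP 4, a patient who stops early for radiological progression is evaluable and counts as one of the 15. Under the SAP 2.4 sentence the same patient does not count. The SAP has no rule saying which section prevails. The trial is open-label, so the choice could be made with responses already known.

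Reading the sentence narrowly, as status at Week 12 only, does not remove the conflict. A patient whose Week 12 scan shows progression has the Week 12 assessment and is therefore in the SAP 4 set.

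At stake is whether the early-stopping probability in the plan describes the rule that will be applied. If 15 non-progressors were required, an ineffective combination would be less likely to stop at stage 1, and more patients would be treated before the look.

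**Working it through.** **Inputs.** From SAP 2.4 Cohort A: p0 = 0.05, p1 = 0.18, 15 + 15 patients, continue if X1 ≥ 1, reject if X1 + X2 ≥ 4. The documents give no Week 12 progression rate, so the excluded share d is an assumption, run from 10% to 50%.

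**1. The plan's own figures (exact binomial).**

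- Early stopping under the null: P(X1 = 0) = 0.95^15 = 0.4633 (stated 46%).
- Type I error: sum over x1 ≥ 1 of P(X1 = x1) × P(X2 ≥ 4 − x1). At p = 0.05 this is 0.3658 × 0.0362 + 0.1348 × 0.1710 + 0.0307 × 0.5367 + 0.0055 = 0.0582 (stated 6%). The last term is P(X1 ≥ 4).
- Power: the same sum at p = 0.18 gives 0.8002 (stated 80%).

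**2. Which patients these figures describe.** The calculation uses only sample sizes, cut-offs and response rates. It gives the same answer for any 15 patients to whom the 5% and 18% apply, so it cannot show who is counted. That comes from the text: SAP 7.1 places the primary ORR analysis on the efficacy-evaluable set, and SAP 4 puts early radiological progressors in that set.

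**3. Sentence followed, stage 1 not refilled, no excluded patient a responder.** Removing non-responders leaves the number of responses unchanged, and the rule asks only whether that number is at least 1. The decision is the same in every case, and null early stopping stays at 46.3%.

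**4. Sentence followed, stage 1 refilled to 15 non-progressors, no excluded patient a responder.** The null response rate among counted patients becomes 0.05/(1 − d). Early stopping is (1 − 0.05/(1 − d))^15, and the average number treated is 15/(1 − d). For d = 20%: 0.05/0.80 = 0.0625; 0.9375^15 = 0.380; 15/0.80 = 18.8.

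**5. Type I error under refilling: two branches.**

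- Final test on 30 treated patients including progressors: the error cannot exceed the single-stage value P(X ≥ 4 | 30, 0.05) = 0.0608, because a futility stop can only remove rejections.
- Refilled stage 1 set carried into the final test of at least 4 of 30: repeat the sum in step 1 with 0.05/(1 − d) in stage 1 and 0.05 in stage 2 (last column).

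| Excluded d (assumed) | Null rate among counted | Null early stopping | Average treated, stage 1 | Type I error, refilled set carried forward |
|---|---|---|---|---|
| 10% | 5.56% | 42.4% | 16.7 | 6.9% |
| 20% | 6.25% | 38.0% | 18.8 | 8.3% |
| 30% | 7.14% | 32.9% | 21.4 | 10.4% |
| 40% | 8.33% | 27.1% | 25.0 | 13.5% |
| 50% | 10.0% | 20.6% | 30.0 | 18.3% |

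The target alpha is 0.10; the last column passes it at about 30% excluded.

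**The case against.** The strongest reply is that the sentence is a leftover with little practical effect. Protocol Appendix C shows nearly the same sentence in synopsis text that has since been replaced, and the rest of the plan agrees on the other rule. No passage provides for replacing progressors. Protocol 5.2, SAP 2.2 and SAP 9.1 replace non-evaluable patients, but early progressors are evaluable under SAP 4, and protocol 8.2 bars replacing treated patients outside the run-in. Without refilling, and with no responder among those dropped, the go/no-go decision is identical.

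Much of this stands. Refilling is inferred from reading the exclusion together with a count out of 15, so every figure in the table is conditional. But the sentence is current SAP text, in the section that sets the Cohort A rule, and its likely origin does not decide which rule applies.

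The unevaluable half of the sentence is also defensible. It fits the replacement of non-evaluable patients, and it may cover a Week 12 scan scored as not evaluable, which SAP 4 does not clearly address.

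A reader might infer that the sentence could discard a true responder, such as a patient with unconfirmed progression at Week 6 and iPR at Week 12, and so raise the chance of wrongly stopping. The documents do not support this on scheduled scans. ORR requires a confirmed response, confirmation comes at least 4 weeks after the first response, and scans fall at Weeks 6 and 12. That patient is not a confirmed responder by Week 12 under either rule.

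**Conclusion.** The contradiction is certain and lies in current text: the progression clause in SAP 2.4 Cohort A conflicts with SAP 2.2 and 4, the second interim sentence of SAP 9.5, the protocol synopsis and protocol 10.5. The stated figures are correct for the efficacy-evaluable set.

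The consequence is conditional. It is nil without refilling if no dropped patient is a responder. With refilling and assumed exclusions of 10% to 50%, the futility look weakens as tabulated.

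A reader might go further in two directions, and neither is supported. One is that 46%, 6% and 80% by themselves prove that progressors are counted. They do not: the replaced synopsis text in Appendix C set almost the same exclusion beside the same three figures. The other is that type I error is out of control. The sentence concerns futility only, and the error exceeds the 10% target only if stage 1 is refilled, the refilled set is carried into the final test, and about 30% or more are excluded.

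This should be fixed because a go/no-go rule is stated in two incompatible ways and the correction is nearly free.

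**What to change.** In SAP 2.4 Cohort A, delete the progression clause. Keep the unevaluable part only if it is aligned with SAP 4, including how a Week 12 scan scored as not evaluable is handled. State that the 15 and the 30 are efficacy-evaluable patients as defined in SAP 4, with early progressors counted as non-responders unless they have a confirmed iCR or iPR.

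In SAP 2.2 and 9.5, align the sentence that times the interim on 15 patients enrolled and followed for 12 weeks, which omits progressors, with the SAP 9.5 sentence that includes them. Until that is done, a bare cross-reference to SAP 9.5 would carry a second inconsistency.

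The cost is a SAP revision of a few sentences, with no recalculation, extra patients, procedures or protocol amendment. Protocol 5.2 and 10.5.1 carry the same shorter timing sentence and can be aligned at the next amendment, which needs IRB/IEC approval.

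Two neighbouring matters are separate and should be reconciled on their own: early progression is called radiological in SAP 4, clinical in protocol 10.3 and is unqualified in the synopsis; and the replacement statements in protocol 5.2, SAP 2.2 and SAP 9.1 do not sit easily with protocol 8.2.
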